AIM 2. Conduct a pilot randomized multicenter trial. Participants (90) will be enrolled at the UF and MC. Patients will be randomized to receive counseling about thyroid biopsy with the conversation aid or routine counseling without it. We hypothesize that conducting a larger efficacy trial and evaluating the effects of using the conversation aid on SDM and rate of unnecessary thyroid biopsies is feasible.

The resulting evidence will serve as proof of concept for the use of a SDM conversation aid to improve the care of patients with thyroid cancer and preliminary evidence for larger efficacy trial.

Research Plan

We hypothesize that the use of a conversation aid in patients with thyroid nodules will enhance the collaboration between patients and clinicians, supporting SDM and lead to adequate and careful selection of patients that should undergo thyroid biopsy in accordance with current clinical practice recommendations. If successful, this innovative intervention will help close the gap between practice recommendations and adequate selection of patients for thyroid biopsy.

In this proposal, we plan to use tools from communication and implementation science to update our conversation aid. The updated prototype will be used on a pilot feasibility, Hybrid 1 study design in which we aim to understand the barriers to implementation (following the Consolidated Framework for Implementation Research Construct) at the same time as we assess feasibility and obtain preliminary estimates of efficacy.

The sample size that is provided for each aim is the total recruitment goal for both centers, with the goal of recruiting half of the patients at each site.

AIM2. Conduct a pilot randomized multicenter trial using the updated conversation aid to assess feasibility and obtain preliminary estimates of efficacy for a larger clinical trial.

In order to understand the extent to which a conversation aid will support SDM and allow for a better selection of patients for thyroid biopsy, a large multicenter randomized trial would be required. In order to obtain information about the feasibility of conducting such trial and preliminary information about outcome effects that can serve as scientific premise, we will conduct a pilot feasibility study.

Settings. The Endocrinology, Ear, Nose and Throat (ENT) and Surgery Clinic at the University of Florida, FL and the Division of Endocrinology at MC, MN.

Participants and identification procedures.

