Measurements and Outcomes. The main outcome of AIM 2 (pilot study) is to determine if conducting a larger study introducing a conversation aid for patients with thyroid nodules is feasible. This pilot study will allow us to test the performance characteristics and capabilities of study designs, measures, procedures, recruitment and operational strategies that can inform the design of a larger study. To achieve this aim we will measure the following outcomes using collected data from recordings of the medical visit, post visit survey during the day of the visit and 6-9 months for patients and at baseline and after each encounter for clinicians, and medical record review). To easy participation, surveys can be completed using printed versions in person/mail or electronic.

1. Feasibility of trial procedures. We will measure the proportion of eligible patients after review of upcoming clinical visits, enrollment and refusal reasons, ability to randomize patients and tolerability by patients and clinicians of the required assessments (time to complete assessments and obtain complete assessment at 6-9 months of follow up). This information will be obtained from adequate documentation and collection of data in pre-designed electronic forms.

2. Feasibility of using the conversation aid in clinical practice (implementation of the intervention in clinical encounters). We will evaluate the recording of clinical encounters to assess fidelity of use of the conversation aid. We will review the recordings of the control group to assess for contamination. Contamination refers to a clinician who, having used the conversation aid with a prior patient, is able to recreate elements of the conversation aid with a subsequent patient allocated to receive usual care. If there is lack of fidelity with the intervention or contamination in the control group, this would require further exploration and possible changes in the study design of a larger trial.

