Sample size. Our primary interest is precise estimates of feasibility and acceptability, as well as outcome variability that will aid planning a larger efficacy trial. We plan to enroll up to 90 patients. A sample size of 41 patients per group will allow us to be relatively precise in our conclusions of feasibility outcomes. If we observe a 15% attrition rate out of 41 patients in the intervention group, the 95% confidence interval (CI) for that rate would be (4%, 26%). While this number of patients is insufficient for a definitive answer about efficacy, it allows us to ascertain the following differences, assuming equal variances and alpha of 0.05, we will have 80% power to detect the following differences: 1. For risk communication, based on our previous study approximately 45% of patients in the control group should be able to identify their thyroid cancer risk; with a sample of 41 patients per arm, we will be able to detect a 30% difference and 2. If we estimate that there is adequate selection for thyroid biopsy according recommendations in 60% of patients in the control group, with a sample size of 41 patients per arm we will be able to detect a 27% difference.

In terms of feasibility for patients, the Division of Endocrinology at UF, performs more than 500 thyroid biopsies annually. At the Mayo Clinic, nine clinicians perform more than 750 thyroid biopsies annually.

We have the support of the faculty of both divisions; as such enrolling 3-5 patients per clinician (30-75 clinical encounters), during a 8-month period is feasible. (AIM 1). Similarly, enrolling 90 patients during an 18-month period is feasible for the pilot randomized trial (AIM 2).

The introduction of a conversation aid into clinical practice and the time required for patient enrollment and interview can disrupt clinical flow. KER unit investigators have used the proposed methods for 15 years and we successfully followed these methods during the development of our prototype.

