Contamination can result from physicians modifying their usual care practice given exposure and use of the conversation aid. Although possible, implementation of SDM in clinical practice has been a challenge suggesting clinicians do not perform these activities without the use of a conversation aid. Moreover, previous studies randomizing at the clinical encounter level have found no evidence of contamination.⁸⁶ Nonetheless, we will assess for contamination by quantifying the degree of elements of SDM noted in the control group. If contamination is noted, we will consider alternative research designs, e.g., a stepped-wedge approach by which clinicians evaluate patients as usual and start using the conversation aid at randomly selected intervals.

Statistical analysis. The distribution of study variables will be described (using frequencies for categorical variables and measures of central tendency for continuous variables) and compared using relative (relative risk) or absolute (mean differences) measures of association and their 95% CI. For the

primary aims of this study related to the feasibility of conducting a larger RCT, we will calculate the rate of successfully completing each of the identified outcomes and calculate the appropriate 95% CI. For the secondary outcomes, we will follow the intention to treat principle.

We will use standard techniques appropriate for trials, with each outcome compared between study arms using t-tests for continuous outcomes and chi-square tests for dichotomous outcomes. If there are differences in baseline characteristics found by statistical means or found to have clinical relevance between the two study groups, these will be accounted for using regression models which include an indicator for study arm.

Similarly, we anticipate evaluating (as done on previous studies) the potential clustering effect of clinicians evaluating a different number of patients. In addition, we are collecting multiple clinical variables, that can potentially affect outcomes, but in this pilot study will only serve as hypothesis generating.

Data management

Patients approached by study staff that agree to participate will be captured in the remote data capture system (REDCap). Potential eligible patients found to be ineligible or eligible but who decline participation will be captured as well. The reason for ineligibility or reason for decline will be captured along with patients' age, sex, and race/ethnicity.

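### Contamination is defined as carry-over after a clinician has used the aid, but the planned assessment takes no account of prior use, so a rate over all control recordings would be diluted.

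*Combined protocol and SAP*

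**What the plan says.** Measurements and Outcomes, item 2 (feasibility of using the aid in practice), sets out both the review and the definition. The review is unrestricted: "We will review the recordings of the control group to assess for contamination". The definition is conditional: "Contamination refers to a clinician who, having used the conversation aid with a prior patient, is able to recreate elements of the conversation aid" for someone seen later in the usual-care arm.

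The contamination paragraph just before Statistical analysis describes the measure differently: "we will assess for contamination by quantifying the degree of elements of SDM noted in the control group". It adds that, if contamination is noted, other designs such as a stepped wedge will be considered for the larger trial.

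Statistical analysis says of the feasibility outcomes: "we will calculate the rate of successfully completing each of the identified outcomes and calculate the appropriate 95% CI". It states no denominator for contamination.

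No section mentions visit order, a count of earlier uses, the number of AIM 2 clinicians or the caseload per clinician. Enrollment, randomization and blinding describes a patient-level random sequence and no stratification by clinician. Every clinician sees a demonstration of the aid before the first patient is enrolled.

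**The concern.** The definition creates two kinds of control visit. Visits after the clinician has used the aid are at risk of contamination; visits before first use are not. The assessment treats them alike, with two consequences.

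- **Rate.** If it is taken over all control recordings, the denominator contains visits that cannot be events. The rate is pulled down, and the interval is computed on more visits than carry information.
- **Degree measure.** SDM elements in a control visit may be carry-over from the aid or the clinician's existing practice. Without a reference level from before first use, the score cannot separate them, so it could also make existing practice look like contamination.

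Feasibility is the main outcome of the pilot, and contamination is one of the few results tied to a named design choice for the larger trial.

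**Working it through.** **1. The plan's own precision figure.** Sample size gives a 95% CI of (4%, 26%) for 15% of 41 patients. The Wald formula gives 0.15 ± 1.96 × √(0.15 × 0.85 / 41) = 0.15 ± 0.109, that is (4.1%, 25.9%). It reproduces. It treats all patients in an arm as the denominator, which suits attrition but not contamination as defined.

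**2. Inputs.**
- Total: "We plan to enroll up to 90 patients" (Sample size).
- Allocation: no ratio is stated. Equal groups are implied by "A sample size of 41 patients per group will allow us to be relatively precise in our conclusions of feasibility outcomes", so 1:1 is assumed, giving about 45 control recordings.
- Number of clinicians J: not stated for AIM 2, so a range is assumed. The AIM 1 figures in Sample size (30 to 75 encounters at 3 to 5 per clinician) imply 30/3 = 10 to 75/5 = 15. A higher value comes from "At the Mayo Clinic, nine clinicians perform more than 750 thyroid biopsies annually" together with "with the goal of recruiting half of the patients at each site": if all nine took part, 45/9 = 5 patients each, and the same load at the other site gives J = 18. Neither source is an AIM 2 enrolment figure.

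**3. Share of control visits before first use.** Let a clinician see m patients under simple 1:1 randomisation. Visit k is a pre-use control visit if it and all earlier visits are control, with probability 0.5^k. Summing over k = 1 to m gives 1 − 0.5^m pre-use control visits, out of m/2 control visits expected. The share is 2(1 − 0.5^m)/m.

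| J (assumed) | m | Pre-use share, equal caseloads | At-risk visits of 45 | Pre-use share, uneven caseloads (simulated) |
|---|---|---|---|---|
| 10 | 9 | 2(1 − 0.5^9)/9 = 22% | 35 | 18% |
| 15 | 6 | 2(1 − 0.5^6)/6 = 33% | 30 | 25% |
| 18 | 5 | 2(1 − 0.5^5)/5 = 39% | 28 | 29% |

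Simulation with equal caseloads gave 22%, 33% and 38%; randomising in blocks of 4 gave 21%, 32% and 38%. The uneven column draws clinician shares from a flat Dirichlet distribution. Participants and identification procedures says up to 50 patients rather than 90; with 50 patients and 10 clinicians, m = 5 and the share is again 39%.

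**4. Effect on a rate.** Rate over all controls = at-risk rate × (1 − pre-use share). The factor is 0.78, 0.67 and 0.61 for equal caseloads and 0.82, 0.75 and 0.71 for uneven ones. For illustration, a 20% at-risk rate would read as 15.6%, 13.4% or 12.2% with equal caseloads.

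**5. Effect on precision.** With zero events, the exact two-sided 95% upper limit is 1 − 0.025^(1/n): 7.9% at n = 45, 10.0% at n = 35 and 11.6% at n = 30.

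**6. Exposure observed.** Visit k follows (k − 1)/2 aid uses on average, so mean prior uses per control visit are (m − 1)/4: 2.0, 1.25 and 1.0 for m = 9, 6 and 5. Uneven caseloads give about 4.2, 2.8 and 2.4 for J = 10, 15 and 18.

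**The case against.** **The plan never fixes the denominator.** It nowhere says that the rate is taken over all control recordings, and applying its definition faithfully would require checking prior use. It also describes a degree rather than a proportion, to which the dilution factor does not apply. This stands: all control recordings is a default reading, not a stated rule. But nothing in the plan calls for prior use to be recorded, and the degree measure has its own gap, the missing reference level.

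**There is no threshold.** The plan acts if contamination is noted, and extra uncontaminated visits remove no event from the numerator. This also stands. A reader might infer that dilution would wrongly lead the larger trial to randomise patients; without a cut-off, the documents do not support that. What is affected is the estimate and its interval.

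**Exposure in a larger trial.** A reader might infer that the pilot has far less exposure than the larger trial would. The documents give no caseload for that trial. By (m − 1)/4, exposure rises only if patients per clinician rise; adding clinicians or sites leaves it unchanged.

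**The pre-use group is not clean.** Clinicians have seen the demonstration, and whether any used the prototype in AIM 1 is not stated. This limits the group to a reference level and does not remove the need to record prior use.

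**Fidelity.** A reader might extend the point to fidelity. Every intervention visit is eligible for fidelity, so no dilution arises there.

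**Small numbers.** With 15 clinicians and equal loads, control visits after 0, 1–2 and 3 or more uses number about 15, 23 and 7. A trend across them would show little, so the breakdown should be descriptive.

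**Conclusion.** The point holds as a mismatch between definition and assessment. Prior use is a condition of contamination, yet the review, the rate and the degree measure all ignore it. On the default reading, a rate over all control recordings is about 0.6 to 0.8 times the at-risk rate, and its interval is too narrow.

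The size rests on assumptions the documents do not settle: 10 to 18 clinicians, 1:1 allocation without stratification by clinician, 90 patients, and use of the aid at every intervention visit. Fewer clinicians, or counting AIM 1 use as prior use, would shrink the pre-use share. More clinicians, or intervention visits where the aid was not used, would enlarge it; 30 clinicians with three patients each would give 58%. This is an inexpensive improvement to the analysis. The documents do not show that the pilot's design conclusion would be wrong.

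**What to change.** - Align the two descriptions of contamination (Measurements and Outcomes, item 2, and the paragraph before Statistical analysis), stating whether the measure is a proportion, a score or both.
- For each control recording, derive the number of earlier actual aid uses by that clinician from visit dates and recordings. Count observed use, not allocation, because fidelity is itself under study. State whether AIM 1 use counts.
- Report the contamination rate and 95% CI over control visits after at least one earlier use, with the denominator stated.
- Show the aid-element score descriptively for control visits before and after first use. Treat the pre-use group as a reference level that has already seen the demonstration.
- Limit any conclusion about patient-level randomisation to the range of prior use observed. Make no statement about exposure in the larger trial unless its patients per clinician are specified.
- Optionally, describe fidelity by order of use.

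The cost is one derived variable and a few sentences of analysis text, using data the trial already generates. The denominator falls from about 45 to roughly 28 to 37 under the assumptions above, so the interval is wider.

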C. Rate of biopsy and distribution according to guidelines recommendations. We will calculate the overall rate of biopsy at the time of visit and at 6-9 months of follow up based on chart review and patient contact. We will compare the rate of biopsy between groups according to guidelines recommendations (categorized as biopsy recommended, consider biopsy, do not perform). These recommendations are based on the size of the nodule and the risk for thyroid cancer. We will expect more variation in the group where biopsy should be considered; but will also explore the availability of the conversation aid to support conversation where thyroid biopsy should not be performed.

D. Worry/Distress. Patients that undergo surveillance for the management of low risk thyroid cancer significantly worry. Significant distress/worry in those choosing observation of a thyroid nodule might limit the implementation of conservative management. To understand the baseline and 6-month level of distress/worry, about a thyroid cancer diagnosis we will use the Impact of Event Scale (IES); a tool of 22 items scored from 0-4. We will also use four questions to assess the degree of worry based on previous studies on thyroid cancer patients (Likert score).

E. Barriers/facilitators: We will collect information regarding length of visit and satisfaction with the decision-making process, as well as fidelity to the use of the decision aid. Additional questions might be added based on the results of the in-depth assessment of feedback from patients and clinicians (AIM 1).

F. Information related to setting up the plan of care: we will collect information through video-graphic analysis in terms of discussion of the diagnostic process and next steps in the plan of care.

We will also include a single item health literacy screening, a 4 item modified subjective numeracy scale and a single item health status measure, to further characterize patients.

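### The 6-9 month distress comparison has no method for missing scores: the named t-test uses only returned surveys and leaves non-returners' earlier score unused

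*Combined protocol and SAP*

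**What the plan says.** Under Statistical analysis: "For the secondary outcomes, we will follow the intention to treat principle". The next paragraph gives the method, "with each outcome compared between study arms using t-tests for continuous outcomes and chi-square tests for dichotomous outcomes". The one alternative is for baseline differences between the arms: "these will be accounted for using regression models which include an indicator for study arm".

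Measurements and Outcomes, item D, gives the purpose and timing of the IES (22 items, each scored 0 to 4): "To understand the baseline and 6-month level of distress/worry". Four Likert questions on worry are added without separate timing; I assume they go in the same surveys. The same section lists the patient survey occasions as "post visit survey during the day of the visit and 6-9 months for patients". No patient survey before the visit is described.

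The summary that closes that section lets patients mail back the post-visit survey or complete it electronically. It limits follow-up at 6-9 months to three contact attempts within two weeks. The Sample size section takes 15% as its example of attrition: "If we observe a 15% attrition rate out of 41 patients in the intervention group".

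The document does not define the intention-to-treat set. It gives no imputation method, repeated-measures model, missing-data assumption or sensitivity analysis.

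**The concern.** A t-test on the 6-9 month score needs that score. Unless an unstated imputation is used, every patient without a follow-up survey drops out of the comparison. The conditional regression does not repair this: it is triggered by baseline imbalance, and a regression on the 6-9 month score loses the same patients.

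The discarded patients are not without information. Only two patient surveys are described, so the first IES appears to sit in the post-visit survey, which most later non-returners should have completed. The plan names no analysis that links the two scores.

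Return of a survey about worry may depend on worry. It may do so differently by arm, because the aid is meant to change who is biopsied and who is observed. Item D says that distress in patients choosing observation could limit conservative management. A difference that partly reflects who answered would then feed into the design of the larger trial.

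**Working it through.** **The plan's own figure.** For 15% attrition in 41 patients, 0.15 ± 1.96 × √(0.15 × 0.85 / 41) = 0.15 ± 0.109, or 4.1% to 25.9%. This matches the stated 4% to 26%. At 15% loss, 41 × 0.85 ≈ 35 patients per arm remain.

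**Assumptions.** The documents give no SD, no correlation between the two scores and no dropout mechanism. I assume standardised scores, correlation r = 0.6, no true arm difference at either time, 45 per arm (90 enrolled), and dropout driven by the post-visit score y₀: logit P(drop) = logit(0.15) + s × y₀, with slope s per SD.

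**Formula.** In each arm the completers' expected 6-9 month mean is r × E[y₀ | stays]. The bias of the t-test is r times the difference in E[y₀ | stays] between arms. Numerical integration over the normal distribution gives:

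| s | Attrition in that arm | E[y₀ given stays] |
|---|---|---|
| 0 | 15% | 0 |
| ±0.5 | 16% | ∓0.078 |
| ±1 | 19% | ∓0.164 |

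**Bias in the arm difference.**
- Dropout related to distress in one arm only: 0.6 × 0.078 = 0.05 SD (s = 0.5); 0.6 × 0.164 = 0.10 SD (s = 1).
- Opposite directions: 0.6 × 0.156 = 0.09 SD (s = ±0.5); 0.6 × 0.328 = 0.20 SD (s = ±1).
- Same slope and rate in both arms: 0.

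Simulation with 5,000 trials per setting agrees: 0.10 SD and 0.19 to 0.20 SD for the opposite-direction cases, with type I error about 14% in the larger one. In the one-arm case with s = 1, type I error is about 7%. An estimator that uses both scores has bias below 0.01 SD throughout.

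**Range over the correlation.** A separate simulation used 41 per arm, r = 0.3, 0.5 and 0.7, and slope 1.
- 15% dropout in each arm, opposite directions: bias 0.08, 0.13 and 0.18 SD; type I error 6.6%, 9.0% and 11.8%.
- 4% against 26% dropout, higher scores more likely to leave in both arms: bias 0.06, 0.09 and 0.12 SD; type I error 5.7%, 6.8% and 7.9%.
- Same rate and mechanism in both arms: bias about 0.

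**Precision under random dropout.** Using both scores multiplies the standard error by roughly √(1 − r² × d), where d is the dropout rate. For r = 0.6 and d = 0.15 this is √(1 − 0.36 × 0.15) = 0.973, a gain of about 3%; the simulation gave 0.230 against 0.223 SD. At 26% dropout the simulated standard error falls from about 0.257 to 0.255, 0.248 and 0.242 SD for r = 0.3, 0.5 and 0.7, a gain of about 1% to 6%.

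**The case against.** A reader might infer that the t-test contradicts the intention-to-treat promise. The documents do not support that. They neither define the term nor say that only completers will be analysed. If it means analysing patients as allocated, the t-test complies. What stands is an omission: the promise has no method behind it for a missing 6-9 month score.

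A reader might also infer that any link between distress and survey return biases the comparison. It does not. With no true difference and the same mechanism in both arms, the bias is about zero. Opposite slopes are the most adverse pattern, and nothing in the documents points to them. With slopes in the same direction but unequal (0.5 against 0.25, or 1 against 0.5), the bias at a 15% base rate is only 0.02 to 0.05 SD.

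Third, it is an inference that the first IES is in the post-visit survey, since item D says only baseline. That survey can also go unreturned, perhaps by the same patients who are lost later. The simulations assume it is complete, so near-zero bias is a best case.

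Finally, imprecision dominates. A bias of 0.10 SD compares with a 95% confidence half-width of 1.96 × 0.230 = 0.45 SD. The plan warns that pilot estimates are imprecise, disclaims a definitive answer on efficacy, and counts completion of the 6-9 month assessment as a feasibility outcome, so attrition will be visible. All this limits the weight of the point. It does not fill the gap: the plan's warning concerns small samples, not selective non-response.

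**Conclusion.** The concern holds as a gap in the analysis plan. For the 6-9 month IES and worry scores, the named test uses returned surveys only and leaves the earlier score of non-returners unused. At attrition near the plan's own example, the plausible bias runs from zero (same mechanism in both arms), through about 0.05 to 0.10 SD (one arm only), to 0.10 to 0.20 SD (opposite directions). Under random dropout the cost is about 1% to 6% in standard error. These sizes rest on an assumed correlation, an assumed logistic dropout model and a complete post-visit survey; none of the three is given in the documents. The point is minor to moderate: it concerns one secondary outcome in a feasibility pilot, and the stated sample size, confidence interval and detectable differences are unaffected.

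**What to change.** Define the intention-to-treat set as all randomised patients, analysed as allocated. Replace the 6-9 month t-test for the IES and worry scores by a mixed model for repeated measures, stating how the four worry items are scored:

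- outcomes: the post-visit and 6-9 month scores;
- fixed effects: arm, time and arm-by-time, with unstructured covariance;
- patients: all randomised patients with at least one score;
- report: the arm difference at each time with its 95% CI.

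State which survey carries the first IES. If it is the post-visit survey, do not enter that score as a baseline covariate: it follows allocation and the aid may already have affected it. Multiple imputation by arm with the post-visit score is an acceptable alternative.

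Add two sensitivity analyses: the completers' t-test, and a missing-not-at-random analysis that shifts the unobserved 6-9 month scores, by arm, over a range fixed in advance.

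The cost is a paragraph of wording and one standard model, with no new data. The downside is that the model assumes missingness is explained by arm and post-visit score, and it gains nothing for patients who return neither survey.

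### Whether the overall biopsy-rate comparison is adjusted for guideline category depends on chance imbalance and an unstated cut-off, not on how well category predicts biopsy

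*Combined protocol and SAP*

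**What the plan says.** Under Measurements and Outcomes, item C, the plan states: "We will calculate the overall rate of biopsy at the time of visit and at 6-9 months of follow up". It then adds a comparison by category: "We will compare the rate of biopsy between groups according to guidelines recommendations (categorized as biopsy recommended, consider biopsy, do not perform"). Category is a baseline feature of the nodule: "These recommendations are based on the size of the nodule and the risk for thyroid cancer".

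The Statistical analysis section sets one default for all outcomes, "with each outcome compared between study arms using t-tests for continuous outcomes and chi-square tests for dichotomous outcomes", with results "compared using relative (relative risk) or absolute (mean differences) measures of association and their 95% CI". Baseline variables enter a regression with an arm indicator only "If there are differences in baseline characteristics found by statistical means or found to have clinical relevance between the two study groups".

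No threshold is given for either limb of that condition, and no covariate is named. Nor does the plan say whether the adjusted or the unadjusted result is the main one once the condition is met. The section on enrollment, randomization and blinding mentions no stratification by guideline category, and says that analysts and statisticians are not blinded.

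**The concern.** In a randomised trial, baseline differences between arms arise by chance. A covariate improves precision because it predicts the outcome, not because the arms happen to differ on it. Guideline category exists to say who should be biopsied, so it is the obvious candidate predictor of biopsy. The plan would nevertheless leave it out of the overall comparison in most trials, or include it in about half, depending on a cut-off that nobody has written down and that unblinded staff would choose.

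The by-category comparison does not fill the gap. It yields three small-sample differences, and no pooled estimate is stated. The Specific Aims name "evaluating the effects of using the conversation aid on SDM and rate of unnecessary thyroid biopsies" as work for the larger trial, so the pilot's biopsy data have a use beyond description. At stake are some precision and a clearly identified main estimate.

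**Working it through.** **1. The plan's own figure.** From Sample size: 41 per arm, 60% versus 87% adequate selection, alpha 0.05 (two-sided reproduces the stated power).
z = (d√n − 1.96√(2p̄q̄)) / √(p₁q₁ + p₂q₂), with p̄ = 0.735.
d√n = 0.27 × 6.403 = 1.729; 1.96 × √0.38955 = 1.223; √(0.24 + 0.1131) = 0.594.
z = (1.729 − 1.223)/0.594 = 0.85, so power is 80%. The sample-size figure reproduces and is not in dispute.

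**2. How often the rule would adjust.** Simulated unstratified 1:1 allocation, 45 per arm (90 in all), four assumed mixes of recommended/consider/do not perform: equal thirds, 50/25/25, 20/60/20, 60/30/10.

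| Trigger | Trials adjusted |
|---|---|
| Chi-square of category by arm, p < 0.05 | about 5% |
| That, or ≥ 20 points in some category's share | 10-14% |
| That, or ≥ 15 points | 23-32% |
| That, or ≥ 10 points | 47-57% |

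Biopsy rates play no part in this table: the trigger ignores prognostic strength.

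**3. What fixed adjustment gains.** The estimate is the Mantel-Haenszel risk difference, Σwₖdₖ/Σwₖ with wₖ = n₁ₖn₀ₖ/(n₁ₖ + n₀ₖ). With shares sₖ, category biopsy rates pₖ, overall rate p and no arm effect, the proportional cut in standard error (SE) is roughly 1 − √(Σsₖpₖ(1−pₖ) / p(1−p)), less about 1 point for the two extra parameters.
- Rates 80/50/30%, equal thirds: 1 − √(0.2067/0.2489) = 8.9%; simulated 7.7%.
- Rates 90/50/10%, equal thirds: 1 − √(0.1433/0.25) = 24.3%; simulated 23.3%.
- Rates 60/50/40%, equal thirds: 1 − √(0.2433/0.25) = 1.3%. Simulated −0.5% to +0.5% over the four mixes.
- Rates 50/50/50% (no prediction): SE 1.1-1.4% larger.

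Over the four mixes, 80/50/30% gives cuts of 4-9% and 90/50/10% gives 12-25%. Under the plan's 0.05 test alone, the same eight scenarios give 1-4%. With the 10-point cut-off added they give 3-22%.

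**4. Checking those rates against the 60% in Sample size.** Adequate selection follows from the category rates once the consider group is scored. With one choice scored adequate there, and a 50% biopsy rate in that group, it is s₁p₁ + 0.5s₂ + s₃(1−p₃).
- 90/50/10%: 66-80% with one choice scored adequate, 90% with the consider group excluded, 92.5-96% if either choice counts. None of the four mixes reaches 60%.
- 80/50/30%: 60-70%, 75-79% and 82.5-90% respectively. Only the 20/60/20 mix with one choice scored adequate matches: 0.16 + 0.30 + 0.14 = 0.60.

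Seven of the eight scenarios therefore imply 66-96%. Scenarios that do match 60%:

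| Rates | Mix | Scoring of consider | SE cut |
|---|---|---|---|
| 60/50/40% | any of the four | excluded | about 0% |
| 70/60/50% | thirds | excluded | 0.3% |
| 65/50/35% | thirds | one choice adequate | 1.8% |
| 80/50/30% | 20/60/20 | one choice adequate | about 4% |
| 90/70/40% | thirds | only no biopsy adequate | 9% |

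A wider search found other rates matching 60% with larger gains, so 9% is not an upper limit.

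**5. Type I error.** In the 45-per-arm null simulations, rejection was 3.1-4.9% under the plan's rule applied mechanically and 4.8-5.4% under fixed adjustment.

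**The case against.** The strongest reply is that category is already used unconditionally. Item C speaks of calculating the overall rate and specifies the between-group comparison by category. The overall chi-square comes only from the generic wording in Statistical analysis, which never names category as a triggered covariate. Unnecessary biopsy is arguably answered within categories, and the plan itself says "We will expect more variation in the group where biopsy should be considered". This stands in part: a reader might infer that the plan ignores guideline category, and it does not. But the generic wording covers each outcome, category falls under the trigger as a baseline characteristic, and separate comparisons neither adjust nor pool the overall one.

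Second, little depends on it. The main outcome is feasibility, the protocol calls the sample insufficient for efficacy, and the later trial is to be powered on clinically significant differences. That stands and sets the severity.

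Third, the gain is assumed. This also stands. A reader might take 4-25% as the expected saving, but most scenarios behind it do not fit the protocol's own 60%. Misclassification would reduce it further: with 20% of patients misclassified, 4-25% falls to 1-11%. The defect in the rule, no cut-off and no named main result, does not depend on these figures.

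**Conclusion.** The point holds, at low severity. For the overall biopsy rate, adjustment is tied to observed imbalance with no stated cut-off. The same plan could adjust in about 1 trial in 20 or in about half, and prognostic value plays no part in the choice. Fixed adjustment is the better method: it costs about 1% in standard error at worst. Its benefit is uncertain, about 0-9% in the scenarios tried that match 60% adequate selection, with more possible under some scorings of the consider group. These figures rest on assumed shares and rates, equal arms of 45 and no arm effect.

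A reader might infer that the rule inflates false positives. The simulations do not show that when it is applied mechanically, although the text supplies no mechanical rule. Nor does the point extend to the sample size, the feasibility outcomes, or other secondary outcomes. For adequate selection, the simulated change from adjusting for category ran from about −2% to +10%, depending on scoring.

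**What to change.** For the overall biopsy rate only, at the visit and at 6-9 months, replace the imbalance trigger with wording such as:

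*Whatever the observed balance, the main estimate is the Mantel-Haenszel risk difference over the three guideline categories, with the Mantel-Haenszel relative risk and 95% CIs. The unadjusted result and the by-category rates are shown alongside.*

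This pools the comparison already planned in item C and keeps the relative risk named in Statistical analysis. In addition:
- Assign category from nodule features in the chart, without reference to arm or visit recording. The aid itself conveys cancer risk, so risk as discussed at the visit could be affected by allocation.
- Drop baseline significance tests as a trigger, and label any imbalance-driven adjustment as a sensitivity analysis.
- Keep the planned evaluation of clinician clustering for this estimate, for example with clinician-clustered standard errors as a check.

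The cost is a few sentences, one abstraction rule, and about 1% in standard error if category predicts nothing. Sample size, feasibility outcomes and trial conduct are unchanged.
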